Title:

A randomized, double blind, crossover trial comparing fexofenadine to placebo for the treatment of proton pump inhibitor (PPI) refractory gastroesophageal reflux symptoms

Principal Investigator:

[name]

Supervisory Faculty:

[name]

Other Investigators:

[name]; [name]; [name]; [name]

Funding Source:

Stanford University Department of Gastroenterology Esophageal Seed Grant

Aims:

1. Evaluate the efficacy of fexofenadine in the treatment of proton pump inhibitor (PPI) refractory gastroesophageal reflux disease (GERD).
2. Evaluate side effects and tolerability of fexofenadine in a population of treatment refractory GERD patients.

Background and Rationale:

About 18-28% of North American adults have GERD at least once per week (1). Proton pump inhibitors (PPIs) are common treatments, but as many as 60% of GERD subjects experience heartburn despite use (2-6). While residual acid exposure may play a role in some patients, PPIs are quite effective at reducing acid reflux (7-10). Another possible explanation is that the persistent heartburn represents neuropathic pain. One potential mechanism includes activation of transient receptor potential channel vanilloid subfamily member 1 (TRPV1) (11). These channels are known to be activated by mechanoreceptors (11) and balloon distension can induce heartburn in healthy volunteers (12). In addition, expression of TRPV1 messenger RNA and protein in esophageal mucosa from subjects with both erosive and non-erosive GERD was significantly higher than that in from health subjects (12).

Recently, histamine has been found to sensitize TRPV1 in rectal biopsy specimens from subjects with irritable bowel syndrome via an action mediated by histamine H1-receptors (13). Moreover, in subjects with irritable bowel syndrome, a histamine H1-receptor antagonist reduced visceral hypersensitivity and abdominal pain and increased symptom relief (13).

Fexofenadine is a histamine H1-receptor antagonist that is available over the counter for relief of allergy symptoms. It has a good safety profile and is generally well tolerated (14, 15). We propose to examine the ability of Fexofenadine to relieve heartburn in GERD subjects who experience heartburn or acid regurgitation despite treatment with a PPI.

Significance:

Minimal therapy exists for PPI-refractory GERD, despite being a very common disorder. If positive this trial will potentially add a valuable, safe, and widely available agent for adjunctive therapy.

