Secondary Outcomes: Mean GERD-HRQL questionnaire score, Mean symptoms severity score (on a scale of 0-4), side effects, mean percentage of days on which rescue medications are needed, patient medication preference.

Statistical Considerations:

Sample Size: Sample size estimation was made referencing a trial evaluating GERD patients refractory to lansoprazole 30 mg daily. Patients in this trial were then randomized to treatment with lansoprazole twice daily or esomeprazole once daily. The mean percentage of GERD free days in the twice daily lansoprazole group was 57.5% (standard deviation 34.8%) (16). For the purposes of our trial with fexofenadine, we considered an additional 50% reduction in percentage of days with symptomatic GERD as a clinically significant endpoint (or mean percentage of GERD free days of 78.75%). Using alpha = 0.05 and beta 0.8 with paired means we calculated a needed sample size of 24 patients. *Our overall goal will be to recruit 40 patients to allow room for error.*

Data Analysis: We plan to analyze all data using a paired t-test comparing response to fexofenadine to response to placebo for each individual patient, provided data has a normal distribution. If not, then paired non-parametric analysis will be used. We will look specifically at the last week of treatment as we expect the drug to take a few days to build up to maximal effect. Drug preference will be compared using Fisher's exact test. Side effects will be compiled into a table to assess for major differences between fexofenadine and placebo.

Outline of key procedures/visits:

Recruitment:

Patients with potential proton pump refractory GERD will be contacted by phone or e-mail to assess interest, or recruited during office visits. Patients presenting to GI clinics will be pre-screened for potential recruitment. The decision to offer enrolment will be up to the treating physician. If the treating physician feels further workup or treatment is needed, then this should be done prior to initiation of the trial.

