Patients will complete an intake questionnaire which will be e-mailed to them via RedCap or secure e-mail, or they will complete the form in person in the office. This intake questionnaire will be reviewed by study staff to determine eligibility to start the run-in period. Prior to run in a subject ID number will be assigned, starting with 1 and increasing sequentially. If a patient presents to an office visit, they will be consented at that time with signatures. If they are contacted by phone/e-mail, they will be provided with the consent form and explanation of the study, but formal consent and signing of the consent forms will take place after the run-in period if they are candidates to continue the study (the run-in week of the study involves no intervention other than questionnaires and is minimal risk).

Run in period (1 week):

1. Patient will take proton pump inhibitor as previously prescribed.
2. Every night before bed patient will record both the number and severity (on a scale of 0-4) of the reflux episodes during the last 24 hours, and need for rescue medications (patients can only use Tums during this trial) in a diary that we provide.

3. On the last day of the period patient will fill out a GERD-HRQL questionnaire about symptoms during the last week.

We will assess by either phone or secure e-mail the number of days on which the patient had symptoms. If the patient had enough symptoms he/she will be invited to participate and to visit the office to sign consent if this was not done at an earlier time. At this point a randomization ID number will be assigned.

Office visit or phone/e-mail conversation (needs to be an office visit if consent has not been signed):

1. Study materials will be collected thus far.
2. Randomization will occur and first drug will be distributed either in person or by mail.

First randomization period (2 weeks):

1. Patient will take proton pump inhibitor as previously prescribed.
2. Patient will also take the study drug (either fexofenadine or placebo) in the morning.
3. Every night before bed patient will record both the number and severity (on a scale of 0-4) of the reflux episodes during the last 24 hours, and need for rescue medications (patients can only use Tums during this trial) in a diary that we provide.
4. On the last day of this period patient will fill out a GERD-HRQL questionnaire about symptoms during the last week.

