5. On the last day of this period patient write down any side effects potentially from the drug
6. On the last day of this period patients will say if they think they received placebo or active treatment

Washout (1 week):

1. Patient will take proton pump inhibitor as previously prescribed.
2. Every night before bed patient will record both the number and severity (on a scale of 0-4) of the reflux episodes during the last 24 hours, and need for rescue medications (patients can only use Tums during this trial) in a diary that we provide.
3. On the last day of the period patient will fill out a GERD-HRQL questionnaire about symptoms during the last week.

Crossover will occur and second drug will be shipped to the patient or distributed at the office. We will touch base with the patient either by phone/in the office/or by secure e-mail at this time.

Crossover (2 weeks):

1. Patient will take proton pump inhibitor as previously prescribed.
2. Patient will also take the opposite study drug as before (either fexofenadine or placebo) in the morning.
3. Every night before bed patient will record both the number and severity (on a scale of 0-4) of the reflux episodes during the last 24 hours, and need for rescue medications (patients can only use Tums during this trial) in a diary that we provide.
4. On the last day of this period patient will fill out a GERD-HRQL questionnaire about symptoms during the last week.
5. On the last day of this period patient write down any side effects potentially from the drug.
6. On the last day of this period patients will say if they think they received placebo or active treatment
7. On the last day of this period patient will select which drug was most effective.

Office visit or phone/e-mail conversation:

1. Study materials will be collected or mailed/e-mailed to us by the patient.
2. We will ask the patient either in person or by e-mail if they have questions and check in on how they are doing from a medical standpoint.

Drug Acquisition, Storage, and Distribution:

- Drugs will be ordered in batches of 300 from Koshland pharmacy ([name], e-mail [contact], contact [name]). The capsules will look identical.
- There will be an un-blinded person ([name]) who distributes the capsules (14 each) into bottles labeled with a code 1 or 2, which corresponds to fexofenadine or placebo. The bottles will also be labeled with subject number.

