- Drugs will be stored at room temperature in a locked cabinet. Storage life is 6 months.
- During distribution a different staff member will distribute the drugs based on a randomization code that contains the subject ID number and the order of the drugs the patient will receive.
- After distribution, on the same randomization sheet the staff member will fill in the patient name, and date the drug is distributed. This will be stored in the same locked cabinet as the drugs.
- The randomization code will be kept by [name]
- We will not be perusing an IND, please see below
 - The IND Regulations [21 CFR 312.2(b)] state that clinical investigation of a drug product is exempt from the requirements for an IND if all of the following apply:
 - The Drug used in the investigation is lawfully marketed in the United States.
 - The investigation is not intended to be reported to FDA in support of new indication for use or to support any other significant change in the labeling for the drug.
 - The investigation is not intended to support a significant change in the advertising of the product.
 - The investigation does not involve a route of administration or dosage level, use in a participant population, or other factor that significantly increases the risks (or decreases the acceptability of the risks) associated with the use of the drug product.
 - The investigation is conducted in compliance with the requirements for IRB review and informed consent [21 CFR parts 56 and 50].
 - The investigation is conducted in compliance with the requirements concerning the promotion and sale of drugs [21 CFR part 312.7], e.g., the drug may not be represented as safe or effective for the purposes for which it is under investigation, nor may it be commercially distributed or sold.

Withdrawal from the study:

- Patients can be withdrawn for the following reasons
 - Side effect possibly related to the study drug
 - Failed adherence to study protocol
 - Discovery that the patient no longer meets inclusion or exclusion criteria
 - Other reasons after discussion with the other investigators

Safety Data:

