The side effects of fexofenadine are minimal and similar to placebo (14, 15). Some side effects that occurred similarly in both the placebo and fexofenadine group include headache, dizziness, upper respiratory tract infection, pharyngitis, rhinitis, sinusitis, nausea, dyspnea, diarrhea, and pain. Patients will be asked to list side effects at the end of each treatment period.

Expected Results:

We suspect the majority of PPI refractory patients in our study will have a component of visceral hypersensitivity given the efficacy of PPIs in reducing acid secretion. Based on prior studies showing efficacy of H1 blockers in IBS, we suspect a similar mechanism will be at play in the esophagus to reduce the sensation of GERD.

Limitations:

This is a small-scale trial and is lacking of pH/impedance data which would better help elucidate the mechanism of GERD. However, such testing would greatly increase cost and reduce patient interest in study participation.

Future Directions:

If positive, future directions include potential collaborations with industry and potential larger scale and longer trials to bring either fexofenadine or similar drugs to market for more widespread use.

Proposed Timeline:

January-February 2018: IRB approval (IRB-44650)

February-December 2018: Recruitment and clinical trial

Jan-February 2019: Data-analysis and manuscript preparation

References:

2. Sontag SJ. Rolling review: gastro-oesophageal reflux disease. *Aliment Pharmacol Ther*. 1993;7(3):293-312.
5. Miner P, Jr., Orr W, Filippone J, Jokubaitis L, Sloan S. Rabeprazole in nonerosive gastroesophageal reflux disease: a randomized placebo-controlled trial. *Am J Gastroenterol*. 2002;97(6):1332-9.

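### The only scheduled side-effect record is one recall entry at the end of each treatment period, and none is scheduled for a patient withdrawn early for a side effect

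*Combined protocol and SAP*

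**What the plan says.** The second aim is to "Evaluate side effects and tolerability of fexofenadine in a population of treatment refractory GERD patients", and side effects are listed among the secondary outcomes.

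**Collection.** Step 5 of both the first randomization period and the crossover period has, on the period's last day only, the "patient write down any side effects potentially from the drug". The Safety Data section says "Patients will be asked to list side effects at the end of each treatment period", which gives the same timing without the reference to cause.

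**Diary.** In the run-in, both treatment periods and the washout, patients "record both the number and severity (on a scale of 0-4) of the reflux episodes during the last 24 hours" and note rescue use. No diary item covers side effects, and the washout steps contain no side-effect entry.

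**Contacts.** At crossover, after the washout, the plan states "We will touch base with the patient either by phone/in the office/or by secure e-mail at this time". After the second period there is a general medical check-in. Neither is described as recording side effects.

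**Withdrawal.** The first listed reason is "Side effect possibly related to the study drug". No form, record of the reason or follow-up is described for that moment.

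**Analysis.** "Side effects will be compiled into a table to assess for major differences" between fexofenadine and placebo. No denominator is given, and nothing is said about withdrawn patients.

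**The concern.** Withdrawal because of a side effect is the clearest tolerability failure that this trial can observe. Under the collection rule, the patient who has one is also the patient who does not reach the day on which side effects are written down. Whether the event is counted then depends on something that the plan does not describe.

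For patients who complete a period, the record is a single free-text recollection of up to two weeks, with no stated recall window. The GERD-HRQL completed the same day is tied to the last week. The period instructions also ask the patient to judge cause before writing anything. A headache or dizziness put down to something else need not be listed, although the Safety Data section names both among the events seen with drug and placebo alike.

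Using the same method on both treatments does not guarantee equal loss. Withdrawals may differ between treatments. Patients also guess their treatment on the same day, and that belief may colour what they attribute to the capsule. At stake is whether the table can carry the tolerability statement that the second aim calls for.

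**Working it through.** **Figures in the plan.** The plan gives no side-effect rate, withdrawal rate or precision target, so there is no figure of its own on this point to reproduce. Its one computed design figure, 24 patients, does reproduce: a paired t-test with difference 78.75 − 57.5 = 21.25, SD of the difference taken as 34.8, two-sided alpha 0.05 and n = 24 has power 0.817. The point does not depend on it. Below, 24 and the recruitment goal of 40 serve only as possible numbers starting a treatment.

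**Following one patient through the rules.** Suppose a patient is withdrawn on day 5 of a treatment period for a side effect.

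1. The step 5 entry falls on the last day of the period. It is not reached.
2. The nightly diary up to day 5 holds reflux episodes, severity and rescue use. It has no place for the event.
3. No contact is scheduled within the two weeks. The next is at crossover, and the plan does not say whether a withdrawn patient is still contacted.
4. The withdrawal section lists the reason but requires no entry.
5. The analysis text does not say where the table's rows come from.

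No step schedules a record of the event, and none excludes it from the table.

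**Illustration with assumed counts.** Let N patients start a treatment, let r = 2 completers report a side effect, and let w patients be withdrawn for a side effect with no entry.

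- Rate shown by the last-day forms = r / (N − w)
- Rate among all treated = (r + w) / N

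| N | w | Forms | All treated |
|---|---|---|---|
| 40 | 0 | 2/40 = 5.0% | 2/40 = 5.0% |
| 40 | 1 | 2/39 = 5.1% | 3/40 = 7.5% |
| 40 | 2 | 2/38 = 5.3% | 4/40 = 10.0% |
| 40 | 4 | 2/36 = 5.6% | 6/40 = 15.0% |
| 24 | 0 | 2/24 = 8.3% | 2/24 = 8.3% |
| 24 | 1 | 2/23 = 8.7% | 3/24 = 12.5% |
| 24 | 2 | 2/22 = 9.1% | 4/24 = 16.7% |
| 24 | 4 | 2/20 = 10.0% | 6/24 = 25.0% |

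With no such withdrawals this loss is zero. The table assumes that withdrawals leave no entry at all, which the documents neither state nor rule out.

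**Direction of a treatment contrast.** Take 40 starters and r = 2 on each treatment, with any withdrawals falling in the second period so that both denominators stay at 40. If w = 4 on fexofenadine and 0 on placebo, the forms differ by 5.6 − 5.0 = 0.6 points and the all-treated rates by 15 − 5 = 10 points. Swapping the treatments reverses the sign, and equal w leaves no difference on either measure. The documents do not say which case applies.

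**Washout.** A side effect can appear or continue after the last capsule. Only the first period is followed by a diary week. Adding washout events to the preceding period would give period 1 three weeks of observation (2 + 1) against two for period 2. That is neutral between treatments only if the two sequences are balanced, and no allocation ratio is stated.

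**The case against.** The strongest reply is that the study team cannot withdraw a patient for a possibly drug-related side effect without knowing of it, and that the analysis text does not confine the table to last-day forms. Both are true. A reader might infer that the plan drops the worst cases from its table. The documents do not say so; they leave unsaid how such cases are recorded and counted.

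A reader might also infer that side effects are recorded only when the patient blames the drug. The period instructions set a lower bar, that of a potential effect, and the Safety Data section sets none. What stands is that the two wordings differ and that one asks the patient to judge cause.

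Nor are events in the first 13 days lost by rule. The last-day entry is not restricted to that day, so completers can list earlier events, and the two later contacts may bring some out. These are still recall and conversation, without a specified record.

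Finally, the table is descriptive, looks only for major differences, and serves a secondary outcome in a trial that calls itself small-scale. That limits how much machinery is justified. It does not argue against an entry at withdrawal, which costs almost nothing.

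**Conclusion.** The gap is real and should be closed. As written, the collection rule schedules no side-effect entry for a patient withdrawn before the last day of a treatment period, relies on one two-week recollection for everyone else, and is worded in two ways. The resulting table may be incomplete, possibly unequally between treatments.

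The size is not computable from the documents. The range from no loss up to 5.6% shown against 15% actual (N = 40, four unrecorded withdrawals) rests on assumed counts and shows the mechanism only.

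Two stronger conclusions are tempting and unsupported. One is that the table is biased toward no difference: unrecorded withdrawals understate the rate on whichever treatment they occur, the attribution wording could act either way, and no documented figure fixes a direction. The other is that small-sample limits measure the defect. With no events in 40 patients, the one-sided 95% upper limit is 1 − 0.05^(1/40) = 7.2%, and with 24 it is 11.7%. These describe imprecision that would remain with perfect collection. It would also go too far to say that the second aim cannot be answered; it would be answered less completely than the trial easily could.

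**What to change.** 1. **Entry at withdrawal.** State that the side-effect form is completed at the time of any early withdrawal, whatever the reason, and that the reason is recorded.
2. **Diary line and wording.** Add one cause-neutral line to the existing nightly diary: any new or worse symptom today, yes or no, and what. Align step 5 of both treatment periods with the Safety Data section by removing the limit to effects potentially from the drug.
3. **Table.** Tabulate events by the treatment being taken. Use as denominator everyone who took at least one dose of that treatment, and give withdrawals for side effects their own row. The two denominators can differ, because a patient who leaves in the first period never starts the other treatment.
4. **Washout.** Show washout events separately and do not add them to period 1, since period 2 has no matching follow-up week.

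The cost is one diary line, slightly more data entry, and more unrelated minor complaints in the table. The first and third changes add no burden for patients who complete. All four belong in the plan before dosing starts, because side effects not recorded during treatment cannot be reliably recovered later.

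### A two-value product code on every bottle, with a dispensing sheet listing each subject's drug order, lets one leaked or inferred key decode all patients for staff who hold the sheet

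*Combined protocol and SAP*

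**What the plan says.** All of the labelling and dispensing text stands under Drug Acquisition, Storage, and Distribution. Capsules are identical in appearance. An un-blinded person puts 14 capsules in each of the "bottles labeled with a code 1 or 2, which corresponds to fexofenadine or placebo". The label has one further element: "The bottles will also be labeled with subject number".

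Dispensing is a separate job: "During distribution a different staff member will distribute the drugs", working from "a randomization code that contains the subject ID number and the order of the drugs the patient will receive". That staff member then adds the patient's name and the dispensing date to the same sheet. On storage of the sheet, the plan says: "This will be stored in the same locked cabinet as the drugs".

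Under Crossover (2 weeks), the second period always uses the other product: "Patient will also take the opposite study drug as before (either fexofenadine or placebo) in the morning". At the end of each treatment period patients list side effects, and "patients will say if they think they received placebo or active treatment"; at the end of the second they also choose the more effective drug. Staff contact each patient by phone, by e-mail or in the office when the second drug is supplied.

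**The concern.** The code denotes the product, and the randomization is carried separately by the order list. A staff member who dispenses therefore holds every subject's coded sequence and lacks one binary fact: which code is fexofenadine. Once that is known for any one patient, it is known for all of them. The subject number on the label does not help, because the product code is printed beside it.

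The stake is expectation bias. Both primary outcomes (GERD-free days and number of episodes), severity, GERD-HRQL, rescue use and preference are all patient-reported, and the Limitations section acknowledges that there are no pH/impedance data. A staff member who knows the allocation and speaks to patients before the second period could convey it without meaning to.

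**Working it through.** **Is the code shared across subjects?** Set the two statements side by side. The label rule ties 1 and 2 to the products. The dispensing rule says that staff "distribute the drugs based on a randomization code that contains the subject ID number and the order of the drugs the patient will receive". If 1 and 2 meant first and second period, the dispenser would need no order list, since everyone would receive 1 and then 2. If the meaning were re-drawn for each subject, a subject-level key would be needed, and none is described. One shared product code is the reading that fits both statements. The words fixed or trial-wide do not appear, so this remains an inference.

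**Reach of one identified bottle.** The inputs are 40 patients (recruitment goal, Statistical Considerations) and 2 treatment periods with one bottle each.
- All bottles: 40 × 2 = 80 (24 × 2 = 48 at the calculated minimum of 24).
- Shared code, person with the sheet or all labels: up to 80 of 80.
- Shared code, patient who sees only their own bottles: 2 of 80.
- Subject-and-period labels, anyone without the list: 2 of 80, because the second period is always the opposite drug.

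The scheme makes a difference only for staff. Completed diaries cannot be biased afterwards. If the key becomes known after k patients have finished, at most 2 × (40 − k) patient-periods are still open: 70 at k = 5 and 60 at k = 10.

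**Can the key be inferred without a leak?** A shared code allows results to be pooled by code. The plan's planning figures give the scale.
- Planned difference: 78.75 − 57.5 = 21.25 points.
- SD: 34.8 points. Taking this as the SD of the within-patient differences, a two-sided paired t-test at 0.05 needs 24 patients for 80% power (power 0.817). This reproduces the plan's 24, so the same SD is used here.
- Standardized effect: 21.25 / 34.8 = 0.61.
- Probability that the code with the better mean is fexofenadine after n completers, assuming normal differences and no period effect: Φ(0.61 × √n).

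| SD of differences (assumed) | n = 1 | n = 5 | n = 10 |
|---|---|---|---|
| 34.8 (reproduces the plan) | 0.73 | 0.91 | 0.97 |
| 49.2 (within-patient correlation 0) | 0.67 | 0.83 | 0.91 |
| 24.6 (within-patient correlation 0.75) | 0.81 | 0.97 | >0.99 |

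The last two rows are a range around an input that the plan does not give: SD of differences = 34.8 × √(2(1 − ρ)), where ρ = 0.5 returns 34.8. The table assumes that the drug works as planned and that someone actually pools diaries by code. With half the planned difference and SD 34.8, the values are 0.62, 0.75 and 0.83; with no effect they are 0.50 throughout. Under subject-and-period labels, staff without the list cannot do this pooling.

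**The case against.** The strongest reply is that nothing has gone wrong unless the key gets out, and the plan takes steps against that: identical capsules, an un-blinded filler separate from the dispenser, a locked cabinet, and a designated keeper of the randomization code. Safety Data describes side effects as similar to placebo, so guessing the code from side effects would be weak. The plan also does not say that the dispenser handles the diaries, guesses or preference forms, so the pooling route is possible but not documented. All of this stands. It bears on how likely a leak is, not on how far it would spread. The plan describes no code-break procedure, yet Withdrawal from the study provides for stopping after a possibly drug-related side effect, so disclosure of one patient's treatment is foreseeable.

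Three stronger readings are tempting and are not supported:
- *That a patient who identifies a bottle unblinds the trial.* That patient learns their own two bottles, exactly as under the alternative labels.
- *That 80 of 80 measures the damage.* It is an upper bound on what a person with full access could decode, and only unfinished diaries can be affected.
- *That the trial is not double blind, or that the dispenser already knows the allocation.* No leak is documented. The sheet gives drug order, but the plan does not say that it names the products, and having a separate un-blinded filler suggests that it uses the codes.

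A further fair point is that the present arrangement divides knowledge: the filler need know only the key, and the dispenser only the order. The alternative gives both to the packer. That is a real cost, and the fix deals with it.

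**Conclusion.** The point holds as a weakness in how the blind is protected, not as a demonstrated failure of it. On the plain reading, the dispensing sheet together with one shared two-value code lets a single disclosed or inferred key decode up to 80 bottles for staff with access, against 2 under subject-and-period labels. The added risk passes through staff who contact patients, and it is confined to diaries still open. The conclusion rests on the inference that the code's meaning is common to all subjects; if it were re-assigned for each subject, the reach would already be 2 and only a clarifying sentence would be needed. The size of any bias cannot be derived from the documents. The change is worth making because the efficacy outcomes are all patient-reported and the remedy is cheap.

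**What to change.** 1. Remove code 1 or 2 from the bottle labels. Use the existing subject number plus Period 1 or Period 2.
2. Have the un-blinded person pack each subject's pair from the sequence list.
3. Take drug order off the dispensing sheet kept in the drug cabinet. Subject number, period, patient name and date are enough to dispense and to keep the record.
4. Keep the list linking subject and period to product away from dispensing and patient-contact staff.

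The cost is new label text, one column fewer on the sheet, and packing by period. The packer, already un-blinded to product, would also learn each subject's sequence and so should have no patient contact. Bottles could not be exchanged between patients, but they already carry a subject number, so little is lost. If the code was in fact meant to vary by subject, the protocol should say so and describe the subject-level key.
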